4.2. Safety Measures

Safety will be measured by assessing all adverse events experienced by patients related or probably related to the study device. Adverse events will be documented at the intra-operative and all postoperative evaluation intervals to determine the safety profile of the device. The incidence of surgery- and device-related events such as device revision, component failure, malfunction, migration, subluxation, dislocation, loosening, nerve damage, deep infection, deep vein thrombosis, pulmonary embolism, or bone breakage/fracture will be collected. Some events may not be evident until after a long-term follow-up such as evidence of severe osteolysis, excessive articular surface wear, or significant debris production. All adverse events in study patients between enrollment and ten years shall be reported at the time of occurrence. Efficacy and safety measurement will be performed as summarized in the study schematic presented in Table 1.

5. Study Population

This clinical study can fulfill its objectives only if appropriate subjects are enrolled. All relevant medical and non-medical Smith & Nephew – Confidential/Study ProtocolR3H01/01Feb2017/Version2.0/BNA including PAS

conditions should be taken into consideration when deciding whether a particular patient is suitable.

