6.3. Telephone Follow-Up

If subjects are unable to return for follow-up visits to the investigator's office, they may be contacted by telephone to assess their status. Subjects will be asked whether the study device is in place or has been revised, and patient satisfaction will be assessed. This information will be recorded on the corresponding CRF.

Document date : 01 Feb 2017; version 2.0 Confidential & Proprietary Page 13 of 25

Post-Approval Study of the R3 Biolox delta Ceramic Acetabular System – Europe	Protocol Number: R3H01/02/01/2017/Version2.0				
	PMA Number P150030				
	ADDENDUM Page: 14 of 25				

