8. SAFETY REPORTING

All adverse events, regardless of their relationship to the study device, occurring from the time of study device implantation through to study completion should be recorded on the appropriate CRFs and reported as below.

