Patient address unknown	Patient is non-compliant with study require	ements				
	Other, please specify:					
Contact the subject by telephone and confirm the information below. If during the discussion Serious Adverse Events are revealed, complete the Adverse Event and Serious Adverse Event case report forms. Record telephone contact in the medical notes.						
Telephone Follow-up						
Unable to contact subject by p	hone during the visit window (No furthe	er response required)				
Ask the following questions an						
1. Has any component of yo	our Smith & Nephew modular hip been i	removed since your last visit?				
Yes No						
Complete Adverse	Event Case Report Form					
2. Have you had any proble	ems with the study hip since the last visit	t to the clinic?				
Yes No						
Complete Adverse	e Event Case Report Form					
3. Do you expect to have the	e study device removed during the next	year?				
Yes No						
Request subject to	contact study coordinator following the ren	noval of device				
4. How satisfied are you wit	h your hip replacement?					
☐ Very satisfied ☐ S	Somewhat satisfied Somewhat dissatis	fied Very dissatisfied				
5. If you had to make the de	ecision again to undergo your hip replace	ement surgery, would you do it again?				
Yes No						
Investigator's Signature:		Date: Month Year				

Plate # 300

smith&nephew

Adverse Event

Project No:			R3
Study Patient No:			

Please complete ONE event form per complica Number each event sequentially beginning wit	h "01" Date of Onset: L. L. L. L. L. L. L. L. L. L. L. L. L.
Event No:	Day Month Year
Adverse Event	
Event / Diagnosis please specify: Severity (Tick one box only) mild moderate severe Serious (Tick one box only) no yes Involves operated side (Tick one box only) no yes not applicable	Outcome of complication (Tick one box only) resolved ongoing / unresolved death, date prosthesis in situ at date of death no, latest date known Removal or revision of component(s), date:
Relationship to study device (Tick one box only) definitely related	Day Month Year
probably related possibly related not related Relationship to study procedure (Tick one box only) definitely related probably related possibly related not related reatment none medication/orthotics	Components removed / revised femoral head femoral stem acetabular cup taper sleeve acetabular liner Hospital (inpatient or outpatient) / Readmission required? no yes, date of readmission:
Investigator's Signature:	Date: Day Month Year

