7.2 Analysis of secondary efficacy endpoints

Secondary endpoints include the following:

- Patient outcomes as measured using the modified Harris Hip Score;
- Radiographic evaluation to assess radiographic success defined as:
 - -No radiolucencies greater than 2 mm in 50% or more in any of the cup or stem zones; and
 - -No femoral or acetabular subsidence greater than or equal to 5mm from baseline; and
 - -No acetabular cup inclination changes greater than 4 degrees (4°) and

These endpoints will be summarized using descriptive statistics and presented for all post-operative visits.

8. Evaluation of Safety

The number of AEs, SAEs, USADEs, Reoperation and Revisions, and the number and the percentage of patients experiencing AEs, SAEs, USADEs will be presented for the enrolled set.

The number of AEs and the number and the percentage of patients with at least one AE will be presented for AEs, and SAEs.

The number and the percentage of patients with at least one AE will be presented by severity, seriousness, device relatedness and procedure relatedness.

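### The telephone follow-up form prompts only for the device, the study hip and satisfaction, although all adverse events must be recorded, so non-hip event percentages may be understated

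*Combined protocol and SAP*

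**What the plan says.** **What must be collected.** Addendum 8 (and main protocol 8, in the same terms) covers "All adverse events, regardless of their relationship to the study device, occurring from the time of study device implantation through to study completion". Main protocol 8, Addendum 6.2 and SAP 3.2 call for an adverse event assessment at each follow-up interval. Main protocol 4.2 names specific events, among them "nerve damage, deep infection, deep vein thrombosis, pulmonary embolism, or bone breakage/fracture will be collected".

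**What a telephone contact asks.** Main protocol 7.5, Addendum 6.3 and SAP 3.2 give the same content: "Subjects will be asked whether the study device is in place or has been revised, and patient satisfaction will be assessed". The Missed Visit/Telephone Follow-up form in the CRF appendix has five questions:

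1. whether any component has been removed;
2. whether there have been problems "with the study hip since the last visit" to the clinic;
3. whether the subject expects to have the "study device removed during the next" year;
4. satisfaction;
5. whether the subject would choose the operation again.

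A yes to question 1 or 2 leads to the adverse event form. Above the questions, the caller is told: "If during the discussion Serious Adverse Events are revealed, complete the Adverse Event and Serious Adverse Event case report forms".

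**What is reported.** SAP 8 states that "the number and the percentage of patients experiencing AEs, SAEs, USADEs will be presented for the enrolled set".

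**The concern.** The collection rule and the collection tool do not match. A caller who completes the telephone form exactly as printed has asked about the hip and nothing else, so the assessment required at that interval has not been made for the rest of the body. Main protocol 12 and SAP 9 list failure to collect adverse events at the defined time points as a deviation, yet following the form produces that result.

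The clinic pages put an open yes/no item on complications since the previous visit. Two subjects with the same history can thus yield different records according to whether they came in or were telephoned. The PAS objective is to confirm that safety is maintained to 10 years, and its adverse event percentages would mix two levels of ascertainment with no means of separating them.

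The primary endpoint is not at risk. Question 1 asks directly about component removal, which is the survivorship event.

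**Working it through.** The documents state no figure on this point, so there is none to reproduce. The check is a comparison of texts, followed by an illustration.

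**Step 1: coverage by type of event.**

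| Event | Clinic form | Telephone form |
|---|---|---|
| Component removal | Prompted | Prompted (question 1) |
| Other study-hip problem | Prompted (open item) | Prompted (question 2) |
| Non-hip, serious | Prompted (open item) | No prompt; recorded if revealed |
| Non-hip, non-serious | Prompted (open item) | No prompt, no recording instruction |

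The open clinic item is legible on the 5- and 7-year pages. The corresponding 10-year page is incomplete in the text available to me, and I assume that it is the same.

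**Step 2: who is affected.** A subject who misses one visit and attends a later one meets the open item there, so the event can still be recovered. The loss falls on subjects with no later clinic visit. No visit is scheduled after year 10, so a telephone contact at year 10 leaves the time since the last attended visit unprompted: three years if that visit was year 7. Under main protocol 5.5 and Addendum 7.2, loss to follow-up requires both two consecutive missed visits and failure to make contact. A subject who answers the telephone therefore stays in the study and could be telephone-only at 5, 7 and 10 years.

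**Step 3: what happens in the analysis.** The adverse event form is completed once per event. The telephone form has no field that separates a subject asked about other events and reporting none from one never asked. SAP 8 gives no rule for the difference.

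**Step 4: illustration of size.** Inputs:

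- N = 135, the number eligible for the PAS (Addendum 3 and 9.2, SAP 3.1 and 3.3).
- f = share telephone-only from year 3 to year 10: not given, assumed 10% to 30%.
- p = share with a non-hip serious event in that time: not given, assumed 30%.
- c = share of those subjects whose event still comes out in the call: not given, taken as 0, 0.5 and 1.

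Subjects missed = N × f × p × (1 − c). Loss in the reported percentage = f × p × (1 − c).

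| c | f = 10% | f = 30% | Loss, percentage points |
|---|---|---|---|
| 0 | 135 × 0.10 × 0.30 = 4.1 | 135 × 0.30 × 0.30 = 12.2 | 3 to 9 |
| 0.5 | 2.0 | 6.1 | 1.5 to 4.5 |
| 1 | 0 | 0 | 0 |

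The result depends on p. With p between 5% and 20% and c = 0, the number missed runs from 135 × 0.10 × 0.05 = 0.7 to 135 × 0.30 × 0.20 = 8.1. The direction is downward, or nil, for every choice of inputs.

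**The case against.** The strongest reply is that the form does provide for serious non-hip events. The instruction to complete the serious adverse event form is not limited to the hip, and an embolism that was life-threatening or led to admission meets the definition of serious. The form also asks why the visit was missed and offers illness as a reason. Main protocol 4.2 requires events to be reported when they occur, whatever the mode of visit, and hospital records are listed as source documents.

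This stands in part. It rules out the reading, which a reader might otherwise infer, that telephone-only subjects are counted as free of thrombosis, embolism and other non-hip events. No section says so. Addendum 9.1 bases categorical percentages on subjects with data and SAP 4.4 provides a category for missing data, so the denominator is open rather than fixed against these subjects. What remains is that capture is passive: an instruction to record what is revealed is not a question. The illness box explains an absence and does not lead to an event form. Reporting at occurrence works only if the site hears of the event, which is least certain for subjects who have stopped attending.

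Two further inferences fail. One is an embolism in the first weeks followed by a missed 3-month visit: Addendum 1.1 and 6.1 treat data to year 3 as already collected, so that case cannot newly arise in the PAS. The other is that the bias must grow as attendance falls, which is plausible but has no attendance figure behind it.

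**Conclusion.** The point holds as an ascertainment gap. Telephone contact prompts for the device, the study hip and satisfaction. Non-hip events enter the record only if they are serious and happen to be revealed, and non-serious ones have no route in through the form. This conflicts with the duty to record all adverse events at each interval and with the open item used in clinic. Non-hip percentages on the enrolled set may be understated, chiefly for subjects whose last contacts are by telephone.

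The size cannot be derived from the documents. A reader might take 3 to 9 points as the expected understatement of the serious event percentage. It is a ceiling for the assumed inputs, because it supposes that nobody discloses. It is also a ceiling for a second reason: SAP 3.6 collects events from implantation, so if the percentage is cumulative, a subject already counted for an earlier event does not lower it when a later one is missed. At half disclosure the figures are 2-6 subjects, and at full disclosure zero. The correction is worth making because it is cheap and bears on the safety results that the PAS exists to report.

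**What to change.** 1. Add one open yes/no question to the telephone form, and matching text to main protocol 7.5, Addendum 6.3 and SAP 3.2, for example: *Have you had any complications, illnesses or hospital admissions since your last visit?* A yes leads to the adverse event form. Keep it open and close to the clinic item. A list of named conditions used only by telephone could make telephone ascertainment more complete than clinic and create a new difference between modes. The recorded no also separates asked-and-none from never asked.
2. In SAP 8, report for each interval how many subjects had adverse events ascertained in clinic, by telephone or not at all, and state the denominator for the adverse event percentages.

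Cost: a CRF and protocol amendment. The addendum says that the original study's forms stay in use, and main protocol 16 and Addendum 10.2 require FDA and ethics committee approval for changes that may affect scientific soundness. In use, it means about a minute per call, more adverse event forms and slightly higher reported percentages. Contacts already made by telephone are not repaired unless the subject is asked again, but the SAP 8 table would at least show how many there are.

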Smith & Nephew Orthopaedics is the sponsor of a prospective, multicenter, non-randomized, clinical outcomes study of the R3 delta Ceramic Acetabular System in patients with degenerative hip disease in Europe. The study was designed to evaluate the performance of the R3 cup with multiple articulation couples including the Biolox delta ceramic-on-ceramic (DOD) and the Oxidized Zirconium-on-crosslinked polyethylene (OxZr/XLPE) articulation couple. The study devices were commercially available in Europe at that time, and the study satisfied EU post-market surveillance requirements. The study was conducted in compliance with ISO 14155 and International Conference on Harmonization Good Clinical Practice (ICH GCP) Guidelines (Notes for Guidance on GCP CPMP/ICH/135/95); National Statement on Ethical Conduct in Research Involving Humans, consisting of a series of Guidelines made in accordance with the National Health and Medical Research Council Act 1992; World Medical Association Declaration Of Helsinki - Ethical Principles for Medical Research Involving Human Subjects October 2008; and 21 CFR 812 revised April 1st, 2008 (Medical Devices), as well as with all applicable local laws and regulations.

2. Study Objectives

The primary objective of this phase of this study is to confirm that the safety and effectiveness of the R3 Biolox delta Ceramic Acetabular System (DOD) is maintained in the long term (to 10 years).

3. Study Design

3.1 General design and plan

This is a prospective, multicenter, observational study that is currently in the follow-up data collection phase. Five of the seven study sites that contributed data to the PMA cohort will participate in this PAS. The two sites that will not participate in the PAS did not enroll any R3 Biolox delta Ceramic Acetabular System (DOD) PMA subjects, as such their data is not suitable for this PAS. The DOD treatment arm of the PMA Cohort included 137 DOD subjects.

Of the 137 DOD subjects included in the PMA Cohort, one died and one was revised by the 3-year follow-up interval. A total of 135 subjects are therefore eligible for this PAS study and all attempts will be made to continue follow-up on all subjects through the 10-year postoperative interval.

Protocol Number: TBD Version 0.3

Forms							
Title	Title Statistical Analysis Plan Template						
Co	Code Version Effective Date Page						
FRM_ST03_032 0.3 23 Apr 2015 6 of 12							

Telephone follow-up for determination of device survival or revision status, and patient satisfaction in cases where subjects fail to return for follow-up visits will be conducted.

3.2 Visit Schedule and Visit Windows

The intervals and schedule of evaluations are provided in the following table.

Study Activity	Preop	Intra-op	D/C	3M	1Y	3Y	5Y	7Y	10Y
							(± 6 Mo)	(± 6 Mo)	(± 6 Mo)
Inclusion/exclusion				1	Already	collec	ted		
Informed consent		Already collected							
Demographics		Already collected							
Modified Harris Hip Score (mHHS)	Already collected x x x								
Radiographic Eval	Already collected x x x								
Adverse Events	Already collected x				Х	X	Х		

Postoperative 5, 7, and 10 Year Visits

At the 5-year, 7-year and 10-year postoperative visits subjects will be evaluated using the modified Harris Hip Score (mHHS). The mHHS includes a modification to the "Distance Walked" section of the Harris Hip Score to replace the number of blocks with actual distances since the term "blocks" is not commonly used as a measurement of distance in Europe.

AP and lateral radiographs will be taken at the 5-year, 7-year and 10-year postoperative visits. Radiographs will be evaluated by an independent evaluator according to a Smith & Nephew R3 Acetabular Hip Study Image Evaluation Protocol.

An adverse event assessment will be conducted at each follow-up interval. Data from each visit will be recorded on the study CRFs.

Telephone Follow Up

If subjects are unable to return for follow-up visits to the investigator's office, they may be contacted by telephone to assess their status. Subjects will be asked whether the study device is in place or has been revised, and patient satisfaction will be assessed. This information will be recorded on the corresponding CRF.

3.3 Sample size justification

Protocol Number: TBD Version 0.3

	Forms						
Title	Title Statistical Analysis Plan Template						
Code Version Effective Date Page							
FRM_S	Т03_032	0.3	23 Apr 2015	7 of 12			

The DOD cohort of the PMA consisted of 137 DOD subjects. The sample size is fixed, based on the number of subjects enrolled in the European Cohort Study. Of the 137 DOD subjects included in the PMA Cohort, one died and one was revised by the 3-year follow-up interval. Thus, a total of 135 subjects are eligible for this PAS study and all attempts will be made to continue follow-up on all subjects throughout 10 years, including telephone follow-up for determination of device survival or revision status in cases where subjects fail to return for follow-up visits.

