Clinical data from this study was used to support a Premarket Approval Application (PMA) that was submitted to the US FDA in August 20, 2015. In the PMA, only data on DOD and OxZr/XLPE subjects were included. Approval was sought for the DOD cohort. The PMA (P150030) was reviewed by the FDA and approved on October 17, 2016. A condition of the approval was that long term follow-up data to the 10-year postoperative interval for the enrolled DOD cohort subjects continue to be reported to the FDA. The original study protocol already included a requirement for subject follow-up to the 10-year postoperative interval, thus no protocol revision of the original study was required. The post-approval study protocol of the DOD cases described in this document describes the long-term follow up requirements included in the original study, and addresses the FDA's requirements for post-approval reporting of clinical study results. Subjects in this post-approval study have already signed informed consent forms agreeing to be followed to the 10-year postoperative interval. No additional consenting is required. Study data for these subjects up to, and including, 3-year follow-up results has already been reviewed in the PMA and is not part of this protocol. The follow- up requirements to the 10-year postoperative interval in the original study protocol have been reviewed and approved by the participating study sites' Ethic Committees (EC). No new subjects will be enrolled. Study data will continue to be collected on the original study's case report forms (CRF).

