9.2. Sample size

The DOD cohort of the PMA consisted of 137 DOD subjects. The sample size is fixed, based on the number of subjects enrolled in the European Cohort Study. Of the 137 DOD subjects included in the PMA Cohort, one died and one was revised by the 3-year follow-up interval. Thus, a total of 135 subjects are eligible for this PAS study and all attempts will be made to continue follow-up on all subjects throughout 10 years, including telephone follow-up for determination of device survival or revision status in cases where subjects fail to return for follow-up visits.

Document date : 01 Feb 2017; version 2.0 Confidential & Proprietary Page 19 of 25

Post-Approval Study of the R3 Biolox delta Ceramic Acetabular System – Europe	Protocol Number: R3H01/02/01/2017/Version2.0	
	PMA Number P150030	
	ADDENDUM Page: 20 of 25	

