4.2 Analysis populations

4.2.1 Enrolled set

All study sites and subjects have been recruited and enrollment is closed. DOD cohort subjects that were included in the PMA will continue to be followed as per the follow-up schedule established in the European Post-market Study until they reach the 10-year postoperative interval.

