4.4 Handling of missing and incomplete data

The number of patients with missing data will be presented under the "Missing" category, if present.

When continuous data are being summarized, only the non-missing values will be evaluated for computing summary statistics.

A sensitivity analysis will be carried out comparing results of the original analysis to the results of an analysis where all missing data are assumed to be failures.

A second sensitivity analysis will be carried out using multiple imputation of the missing data in the form of a tipping point analysis. Multiple scenarios will be analyzed, each with a different number of missing data points imputed as successes for each treatment group. (Missing data points not imputed as successes will be imputed as failures.) The purpose of the analysis is to find the tipping point where a certain number of success imputations for each treatment group causes the inference to reverse.

In general, partial dates will be imputed as follows:

- if only the day is missing, the first day of the month will be assumed;
- if the day and the month are missing, January 1st will be assumed;
- if a date is completely missing or unknown the patient's data will not be included for analysis

Protocol Number: TBD Version 0.3

Forms							
Title	Title Statistical Analysis Plan Template						
Co	Code Version Effective Date Page						
FRM_S	FRM_ST03_032 0.3 23 Apr 2015 9 of 12						

5. Evaluation of Demographic and Baseline Characteristics

Given the nature of this study, the demographic data have been already obtained. The demographic and baseline characteristics will be summarized using descriptive statistics for the Enrolled Set.

6. Patient Accounting

Patient accounting will be presented according to the recommendations in the FDA guidance entitled "Clinical Data Presentations for Orthopedic Device Applications".

- Actual A: Subjects with complete data for the primary endpoint, evaluated per protocol, in the window time frame.
- Actual B: Subjects with any follow-up data reviewed or evaluated by investigator ("all evaluated" accounting).
- Theoretical: Number of subjects that would have reached the beginning of the study window associated with each visit if all subjects returned.
- Deaths: Cumulative number of subjects that died during or prior to the study visit.
- Failures: Cumulative number of subjects that failed (revision) during or prior to the study visit.

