- Expected: Theoretical subjects minus the number of deaths and revisions.
- Follow-up Rate: Actual A/Expected*100

Patients discontinued from the study prematurely will be presented, with a breakdown of the reasons for discontinuation as reported in the CRF.

7. Evaluation of Efficacy

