7.1 Analysis of primary endpoint

The primary endpoint is implant survivorship at 10 years post study procedure.

Since this Post-Approval Study (PAS) is intended to document the long-term survivorship of the DOD treatment group only and no comparison to a control is required, no formal statistical hypothesis testing will be conducted.

Implant survivorship will be measured from time of surgery to time of the first instance of removal of any device component for any reason. Subjects who do not experience a removal for any reason will be censored at the date of last data collection.

Protocol Number: TBD Version 0.3

Forms					
Title Statistical Analysis Plan Template					
Code		Version	Effective Date	Page	
FRM_ST03_032		0.3	23 Apr 2015	10 of 12	

Kaplan-Meier (KM) estimates will be provided by time point (life tables) and graphically (survival curves).

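### Does the SAP leave open whether the 10-year survivorship curve is built on 137 or 135 DOD subjects?

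*Combined protocol and SAP*

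**What the plan says.** Two counts appear for the post-approval study (PAS). The main protocol's Protocol Summary puts the PAS cohort at 137. The Addendum synopsis gives a sample size of 135. Addendum 9.2 states both: "The DOD cohort of the PMA consisted of 137 DOD subjects", then 135 once one death and one revision by year 3 are removed. SAP 3.1 repeats this ("A total of 135 subjects are therefore eligible for this PAS study"), as does SAP 3.3 ("Thus, a total of 135 subjects are eligible for this PAS study").

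The SAP defines one analysis set, the Enrolled set, without a number: "DOD cohort subjects that were included in the PMA will continue to be followed as per the follow-up schedule" (SAP 4.2.1). SAP 7.1 sets the time origin and the event, "Implant survivorship will be measured from time of surgery to time of the first instance of removal of any device component for any reason", and censors everyone else at last data collection. It names no population. SAP 6 counts failures and deaths cumulatively ("Failures: Cumulative number of subjects that failed (revision) during or prior to the study visit") and defines "Expected: Theoretical subjects minus the number of deaths and revisions". Addendum 1.1 says that the data up to year 3 "has already been reviewed in the PMA and is not part of this protocol".

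**The concern.** The 135 are by selection alive and unrevised at 3 years. A Kaplan-Meier curve on those subjects, timed from surgery, would stand at 100% to year 3 by construction. It would leave out the one known revision and present a conditional figure as survivorship from surgery.

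Three things make that reading look possible. The synopsis gives 135 as the sample size. The word eligible is attached to 135. Addendum 1.1 appears to put the first three years outside the PAS. Since neither SAP 4.2.1 nor SAP 7.1 gives a number, nothing seems to stop an analyst from taking 135. At stake are the meaning and reproducibility of the primary estimate that goes to the regulator.

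**Working it through.** **Inputs.** 137 DOD subjects, one death and one revision by year 3 (SAP 3.3). 3-year Kaplan-Meier estimate 99.3%, 95% CI 97.4% to 100.0% (SAP 3.5.1). Numbers of later revisions and losses are assumptions, because the documents give none.

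**1. The plan's own figures.**
- Count: 137 − 1 − 1 = 135, as stated.
- 3-year estimate with one revision: S = 1 − 1/n, where n is the number at risk at that revision. With n = 137, S = 136/137 = 99.27%, which rounds to 99.3%.
- Which n fit: 1 − 1/133 = 99.248% rounds to 99.2%, and 1 − 1/134 = 99.254% rounds to 99.3%. So n lies between 134 and 137.
- The quoted estimate therefore includes the revised subject. A curve on the 135 would give 100% at year 3.
- The lower limit of 97.4% is not reproduced by a plain Greenwood interval, which gives 97.8% with n = 137. The SAP does not name its interval method, and nothing below depends on it.

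**2. The text side by side.**

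| Text | Fits |
|---|---|
| Enrolled set is the DOD subjects included in the PMA (SAP 4.2.1), numbered at 137 in SAP 3.1 and 3.3 | 137 |
| PAS cohort in the Protocol Summary | 137 |
| PAS inclusion rule takes the DOD arm of the PMA cohort (Addendum 5.2) | 137 |
| Time from surgery to first removal (SAP 7.1) | 137 |
| Deaths and failures cumulative (SAP 6) | 137 |
| Adverse events from implantation (SAP 3.6) | 137 |
| Secondary endpoints shown for all postoperative visits (SAP 7.2) | 137 |
| 3-year estimate quoted for the DOD group (SAP 3.5.1) | 137 |
| Eligible for the PAS, tied to continuing follow-up (SAP 3.1, 3.3; Addendum 3, 9.2) | 135, as those still to be followed |
| Synopsis sample size | 135 |

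The 135 is also what SAP 6 yields as Expected before any further event, if Theoretical starts at 137: 137 − 1 − 1 = 135. The two counts are the start of the cohort and the number remaining in it.

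**3. Size of the error if 135 were used.** Let S₁₃₅ be the 10-year estimate on the 135. Including the early revision multiplies it by (1 − 1/n), so the gap is S₁₃₅/n. With n = 137, d assumed later revisions and no other loss, S₁₃₅ = 1 − d/135:

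| d | On 135 | On 137 | Gap (points) |
|---|---|---|---|
| 0 | 100.00% | 99.27% | 0.73 |
| 4 | 97.04% | 96.33% | 0.71 |
| 8 | 94.07% | 93.39% | 0.69 |
| 13 | 90.37% | 89.71% | 0.66 |

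- With n = 134 and d = 0 the gap is 1/134 = 0.75 points.
- With 20% of the 135 lost first (108 at risk) and d = 4: S₁₃₅ = 104/108 = 96.30%, gap 0.70.
- With only 81 at risk and d = 13: S₁₃₅ = 68/81 = 83.95%, gap 0.61.

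For scale, the Greenwood 95% half-width on 137 with d = 4 is 1.96 × 0.9633 × √[1/(137×136) + 4/(135×131)] = 3.16 points.

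**The case for a change.** The strongest case for a change is that the Enrolled set is described by who will continue to be followed. A dead subject cannot be followed, and Addendum 7.2 terminates a revised one, so that description can be read as 135. Addendum 1.1 can be read the same way. The final report is about seven years off and may be written by other staff, and one sentence would settle the matter at almost no cost. If no later revision occurred, the wrong choice would report 100% instead of 99.3%.

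Part of this stands. The synopsis and the Protocol Summary do give different counts, and SAP 7.1 states neither a population nor a number. The rest is weaker. In SAP 4.2.1 the subjects named are those included in the PMA, and no competing set exists for SAP 7.1 to use. Addendum 1.1 explains why no new consent or enrolment is needed. Taken literally as removing the first three years, it would conflict with any curve timed from surgery, on 135 as much as on 137.

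Two further harms could be imagined: Expected falling to 133, and a revision count one short in SAP 8. The first needs the same two exits subtracted twice. The second needs the early revision left out of a set whose events run from implantation.

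With 13 later revisions the two estimates fall on either side of 90%. That 10-year target in main protocol section 3 belongs to the R3 cup in the 500-patient study. The PAS sets no threshold.

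**Conclusion.** No change follows. Followed as written, the SAP gives the sound estimate: 137 subjects from surgery, the early revision as an event and the early death censored. The missing number is a gap in wording that the rest of the document fills, and writing it in would only record what the analysts would do anyway. A mistaken use of 135 would raise the 10-year estimate by about 0.6 to 0.75 points. That range rests on 0 to 13 assumed later revisions, 81 to 135 assumed at risk when they occur, and 134 to 137 at risk at the early revision. The error would also show at once, because the curve would read 100% at year 3 against the SAP's own 99.3%. The PAS has no formal test, so no inference could reverse.
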